  - Continuous or intermittent small molecule therapeutics within a period of time that is  $\leq 5$  t1/2 or  $\leq 4$  weeks (whichever is shorter) prior to starting study drug
  - Any other investigational agents within a period of time that is  $\leq 5$  t1/2 or less than the cycle length used for that treatment or  $\leq 4$  weeks (whichever is shortest) prior to starting study drug
  - Wide field radiotherapy (including therapeutic radioisotopes such as strontium 89) ≤ 4 weeks or limited field radiation for palliation ≤ 2 weeks prior to starting study drug
- 10. Patients who are currently receiving, or are planning to receive during participation in this study, treatment with agents that are known strong inducers or inhibitors of CYP3A4 and medications which increase serum phosphorus and/or calcium concentration are excluded. (Refer to Appendix 2 for list of prohibited medications). Patients are not permitted to receive enzyme-inducing anti-epileptic drugs
- 11. Consumption of grapefruit, grapefruit juice, grapefruit hybrids, pomegranates, star fruits, pomelos, Seville oranges, or products containing juice of these fruits, within 7 days prior to first dose
- 12. Insufficient bone marrow function
  - ANC  $< 1,000/\text{mm}^3 [1.0 \times 10^9/\text{L}]$
  - Platelets  $< 75,000/\text{mm}^3 [75 \times 10^9/\text{L}]$
  - Hemoglobin < 9.0 g/dL
- 13. Insufficient hepatic and renal function

- Total bilirubin > 1.5x ULN (for patients with documented Gilbert syndrome, direct bilirubin ≤1.5x ULN and enrollment requires approval by the medical monitor)
- AST/SGOT and ALT/SGPT > 2.5x ULN (AST and ALT > 5x ULN in the presence of liver metastases)
- Serum creatinine > 1.5x ULN and a calculated (using the Cockcroft-Gault formula [Cockcroft 1976]) or measured creatinine clearance of < 45 mL/min
- 14. Abnormal calcium or phosphorus:
  - Inorganic phosphorus outside of normal limits
  - Total serum calcium (can be corrected) outside of normal limits
  - Calcium-phosphorus product ≥55 mg²/dL²
- 15. Clinically significant cardiac disease including any of the following:
  - Congestive heart failure requiring treatment (NYHA Grade ≥ 2), LVEF < 50% as determined by MUGA scan or ECHO, or uncontrolled hypertension (refer to WHOISH guidelines)
  - History or presence of clinically significant ventricular arrhythmias, atrial fibrillation, resting bradycardia, or conduction abnormality

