# Management of Hyperphosphatemia

Hyperphosphatemia is a recognized on-target effect of potent and selective inhibitors of the FGFR pathway. While on BGJ398, patients should avoid foods that are especially high in phosphate and, if possible, should restrict dietary phosphate to 600 – 800 mg/day. High-phosphate foods include dairy products; meats, nuts, and other high-protein foods; processed foods; and dark colas.

Patients who have experienced hyperphosphatemia should take a phosphate binder such as sevelamer, sucroferric oxyhydroxide, lanthanum carbonate, ferric citrate, etc. within 30 minutes of a meal on the day while taking BGJ398. Once the patient has had hyperphosphatemia, the patient should remain on a low phosphate diet, if possible, and take phosphate binder on the days BGJ398 is taken, even if the serum phosphorus is normalized. Unless otherwise specified by the local package insert or institutional practice, the following regimen should be used to manage hyperphosphatemia:

- For serum phosphorus > 5.5 7.5 mg/dL
  - Start sevelamer 800 mg three times a day with meals
  - Increase the dose of sevelamer up to 1200 mg every 8 hours
- For serum phosphorus ≥7.5 mg/dL
  - o Increase the dose of sevelamer up to 1600 mg (2 tablets per meal) every 8 hours
  - Consider adding acetazolamide two to three 250 mg tablets per day.

During the BGJ398 cycle, patients do not need to be on a low phosphate diet or take a phosphate binder during their 1-week off period unless serum phosphorus is not normalized. Other dose modifications are provided in Table 5, but should be modified as per country or institutional practice.

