### 8.1.2 Laboratory test abnormality

Abnormal laboratory values or test results occurring after informed consent constitute adverse events only if they induce clinical signs or symptoms, are considered clinically

significant, require therapy (eg, hematologic abnormality that requires transfusion or hematological stem cell support), or require changes in study medication(s). Laboratory abnormalities that constitute an Adverse event in their own right should be recorded on the Adverse Events eCRF. Whenever possible, a diagnosis, rather than a symptom should be provided (e.g. anemia instead of low hemoglobin). Laboratory abnormalities that meet the criteria for Adverse Events should be followed until they have returned to normal or an adequate explanation of the abnormality is found. When an abnormal laboratory or test result corresponds to a sign/symptom of an already reported adverse event, it is not necessary to separately record the lab/test result as an additional event.

Laboratory abnormalities, that do not meet the definition of an adverse event, should not be reported as adverse events. A Grade 3 or 4 event (severe) as per CTCAE v4.0 does not automatically indicate a SAE unless it meets the definition of serious as defined below and/or as per investigator's discretion. A dose hold or medication for the lab abnormality may be required by the protocol and is still, by definition, an adverse event.

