2.7.2.1.1 Data Handling

Adverse events will be coded using the Medical Dictionary for Regulatory Activities (MedDRA) version 21.0 and assessed according to the Common Terminology Criteria for Adverse Events (CTCAE) version 4.03, respectively.

The CTCAE represents a comprehensive grading system for reporting the acute and late effects of cancer treatments. CTCAE grading is by defining a 5-point scale generally corresponding to mild, moderate, severe, life threatening, and death. This grading system inherently places a value on the importance of an event, although there is not necessarily proportionality among grades (a Grade 2 is not necessarily twice as bad as a Grade 1).

If CTCAE grading does not exist for an AE, Grades 1, 2, 3, or 4 corresponding to the severity of mild, moderate, severe, and life-threatening, respectively, will be used. CTCAE Grade 5 (death) will not be used in this study. Death information will be collected on the “Death” eCRF pages.

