Minimal critical toxicities to be analyzed under this statistical analysis plan include the following categories:

- Cardiac toxicity including QT prolongation and other ECG abnormalities
- Hepatotoxicity
- Nephrotoxicity
- Hematologic toxicity

Subject incidence of TEAEs indicative of potential cases of the toxicities will be summarized for each of the categories.

For hepatotoxicity, in addition, abnormalities in liver function tests will be summarized. Subject incidence of the following will be provided:

- $3\times$ -, $5\times$ -, $10\times$ -, and $20\times$ upper limit of normal (ULN) elevations of aspartate aminotransferase (AST) and/or alanine aminotransferase (ALT).
- Any elevations of bilirubin; elevated total bilirubin to $\geq 2\times$ ULN.
- Any elevations of alkaline phosphatase (ALP) $>1.5\times$ ULN.
- Elevation of “ALT or AST” ($>3\times$ ULN) accompanied by elevated total bilirubin ($>1.5\times$ ULN, $\geq 2\times$ ULN) and ALP $<2\times$ ULN.

In addition, a listing of potential Hy’s Law cases identified will be provided. Potential hepatotoxicity is identified by the Hy’s Law (FDA Guidance for Industry Drug Induced Liver Injury: Pre-marketing Clinical Evaluation, July 2009) as: ALT or AST $>3.0\times$ ULN; total bilirubin $\geq 2.0\times$ ULN, ALP $<2.0\times$ ULN; and no other confounding factors including preexisting or acute liver disease.

For cardiac toxicity, ECG findings will also be summarized as specified in Section [2.7.3.3](#).

Phosphate Binder Medication

Number of subjects who have taken phosphate binder medication (Section [5.11](#)) and the types of medication will be summarized by the formulation. Of these patients who have taken phosphate binder, number (percentage) of subjects who had a Grade 3/4 hypophosphatemia AE (including preferred terms hypophosphatemia and blood phosphorus decrease) will be summarized.

2.7.2.2 *Laboratory Data*

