2.7.2.2.1 CTC Grading for Laboratory Parameters

Grade categorization of lab values will be assigned programmatically as per NCI Common Terminology Criteria for Adverse Events (CTCAE) version 4.03. The calculation of laboratory CTC grades will be based on the observed laboratory values only; clinical assessments will not be taken into account.

For laboratory tests where grades are not defined by CTCAE v4.03, results will be graded by the low/normal/high (or other project-specific ranges, if more suitable) classifications based on laboratory normal ranges.

A severity grade of 0 will be assigned for all non-missing lab values not graded as 1 or higher for CTCAE parameters that are unidirectional. For CTCAE parameters that are bidirectional non-gradable values which are beyond the normal range will be left missing while Grade 0 will be assigned to the value within the normal range. Grade 5 is not applicable.

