2.7.2.2.3 Data Analysis

The laboratory summaries will include all assessments available for the lab parameter collected no later than 30 days after the last study treatment administration date. Laboratory parameters for hematology and blood chemistry will be summarized at baseline, each post-baseline visit (based on the visit schedule defined in the protocol along with a window), the maximum and minimum observed post-baseline values, and last observed value, along with the change from baseline.

For laboratory tests where grades are defined by CTCAE 4.03:

- Worst post-baseline CTCAE grade (regardless of the baseline status). Each subject will be counted only once for the worst grade observed post-baseline.
- Shift tables using CTCAE 4.03 grades to compare baseline to the worst on-treatment value

For laboratory tests where grades are not defined by CTCAE 4.03, the summary will be based on normal range:

- Worst post-baseline abnormal value (regardless of the baseline status). Each subject will be counted only once for the high/low category.
- Shift tables to compare baseline to worst on-treatment values using the low/normal/high/ (low and high)

For laboratory tests that are graded for both low and high directions, the shift tables and summary of post-baseline abnormal results will be done separately and labeled by direction.

As discussed in ‘Minimum Critical Toxicities’ in Section [2.7.2.1.2](#), incidence of potential drug-induced liver injury based AST, ALT, TBL, ALP will be presented and potential Hy’s law cases will also be listed.

[Table 4](#) provides an example of laboratory parameters for which CTCAE grades are defined, [Table 5](#) provides an example of laboratory parameters for which shift tables were based upon the local lab normal range

Table 4: Example of Laboratory Parameters for Which CTCAE Grades are Defined

| Hematology and Coagulation | Biochemistry | |
|----------------------------|--------------|-------------------------------|
| White Blood Cells (WBC) | ↑ ↓ | Creatinine ↑ |
| Hemoglobin | ↑ ↓ | Sodium ↑ ↓ |
| Platelets counts | ↓ | Potassium ↑ ↓ |
| Absolute Neutrophils | ↓ | Corrected Calcium ↑ ↓ |
| Absolute Lymphocytes | ↑ ↓ | Magnesium ↑ ↓ |
| APTT | ↑ | Albumin ↓ |
| INR | ↑ | AST (SGOT) ALT (SGPT) ↑ |
| | | Total Bilirubin ↑ |
| | | Phosphate ↓ |
| | | amylase ↑ |
| | | lipase ↑ |
| | | Alkaline phosphatase ↑ |
| | | Total Cholesterol ↑ |
| | | Triglycerides ↑ |
| | | Urate ↑ |

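### The SAP specifies no categorical laboratory table for high phosphate, and its LVEF change categories leave gaps and lose order

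*SAP*

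**What the plan says.** **Phosphate.** SAP Table 4 shows phosphate with a downward arrow only, so the SAP treats it as graded in one direction. For such parameters SAP 2.7.2.2.1 states: "A severity grade of 0 will be assigned for all non-missing lab values not graded as 1 or higher for CTCAE parameters that are unidirectional". SAP 2.7.2.2.3 then gives worst-grade and shift tables for tests with CTCAE grades, and low/normal/high tables for tests without them. Its rule for two tables per test begins "For laboratory tests that are graded for both low and high directions, the shift tables", so it covers only tests graded both ways. SAP Table 5, which lists tests summarised by normal range, omits phosphate. Tables 4 and 5 are both headed as examples. The continuous summary includes "the maximum and minimum observed post-baseline values, and last observed value", with change from baseline.

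Hyperphosphatemia is also a subcategory of an AE of special interest. On AE severity, SAP 2.7.2.1.1 says: "If CTCAE grading does not exist for an AE, Grades 1, 2, 3, or 4 corresponding to the severity of mild", and so on through life-threatening. Among patients on phosphate binders, SAP 2.7.2.1.2 counts the "number (percentage) of subjects who had a Grade 3/4 hypophosphatemia AE" and nothing for the high direction.

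The protocol says: "Hyperphosphatemia is a recognized on-target effect of potent and selective inhibitors of the FGFR pathway". Its Table 5 acts on serum phosphorus at >5.5, >7.5 and >9.0 mg/dL. Section 5.3 excludes patients with "Inorganic phosphorus outside of normal limits".

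**LVEF.** SAP 2.7.3.2 defines three clinically significant changes:
1. a fall of >10 to <20 points, with LVEF 40 to <50%;
2. a fall of >=20 points, with LVEF 20 to <40%;
3. LVEF <20%.

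It also plans change-from-baseline summaries, and a shift table of minimum LVEF in classes <40%, 40% to 50%, and >=50%.

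**The concern.** For phosphate, the laboratory effect the protocol expects and manages by measured level is invisible in the only categorical laboratory tables the SAP assigns to it. A reader of a shift table showing Grade 0 to Grade 0 would take it to mean that nothing happened. The AE tables cannot give the level. They count reported events, and if high phosphate has no CTCAE grade, as Table 4 implies, severity is a mild-to-life-threatening judgement and not an mg/dL value. Values of >5.5 to 7.5 mg/dL become AEs only if they are symptomatic, judged clinically significant, or treated.

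For LVEF, fall and level are joined by a logical *and*. A patient whose heart function worsens further can therefore leave the count. The headline count of clinically significant LVEF changes would include milder falls and omit worse ones from the same baseline.

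**Working it through.** **Phosphate: no arithmetic applies, so each specified categorical table is checked in turn.**

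| SAP table | Applies to | High phosphate shown? |
|---|---|---|
| Worst CTCAE grade and grade shift | Tests with CTCAE grades | Phosphate is included, but high values are Grade 0 |
| Low/normal/high worst value and shift | Tests without CTCAE grades | No: phosphate is graded and is not in Table 5 |
| Separate tables by direction | Tests graded both low and high | No: phosphate is graded low only |

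Entry requires phosphorus within normal limits. A patient who is never low and peaks at 10 mg/dL is therefore recorded as Grade 0 at baseline and Grade 0 at worst. That value does reach the AE tables: a single value >9.0 requires a hold under protocol Table 5, and protocol 8.1.2 says: "A dose hold or medication for the lab abnormality may be required by the protocol and is still, by definition, an adverse event".

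**LVEF: rules.** Let b be baseline, f the follow-up value and d = b - f.
- Category 1: 10 < d < 20 and 40 <= f < 50.
- Category 2: d >= 20 and 20 <= f < 40.
- Category 3: f < 20.

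Two combinations meet none of these:
- Gap A: d >= 20 with f >= 40.
- Gap B: 10 < d < 20 with 20 <= f < 40.

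| Baseline | Follow-up | Fall | Category |
|---|---|---|---|
| 65 | 46 | 19 | 1 |
| 65 | 45 | 20 | none |
| 65 | 40 | 25 | none |
| 65 | 39 | 26 | 2 |
| 55 | 40 | 15 | 1 |
| 55 | 39 | 16 | none |
| 55 | 36 | 19 | none |
| 55 | 35 | 20 | 2 |

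**LVEF: extent.** Take integer pairs with b = 50 to 70, f = 20 to 49 and d > 10. The lower limit for b comes from protocol 5.3, which excludes LVEF <50%. The upper limit of 70 is an assumption.
- All pairs: b = 50 to 60 gives 20 + 21 + ... + 30 = 275. b = 61 to 70 gives 10 x 30 = 300. Total 575.
- Gap A, here with f = 40 to 49: b = 60 to 69 gives 1 + 2 + ... + 10 = 55, and b = 70 gives 10. Total 65.
- Gap B: b = 50 to 58 gives 9 + 8 + ... + 1 = 45.
- Uncategorised: 65 + 45 = 110, and 110/575 = 19.1%.
- With a baseline ceiling of 65: 66/425 = 15.5%. With a ceiling of 75: 160/725 = 22.1%.

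At baselines 51-58 and 60-68, which is 8 + 9 = 17 of 21, a further fall takes a patient from counted to uncounted. Baseline 59 has neither gap. At 50, 69 and 70 category 1 is empty, so order is kept but the gaps remain.

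**LVEF: check of the proposed rule.** Give each pair with d > 10 and f < 50 the worse of its fall band and its level band, with f < 20 highest. Every one of the 575 pairs has both bands, so all are categorised. At a fixed baseline, a lower f increases d and lowers the level, so neither band can improve; order is reversed at 0 of 21 baselines. A 2-point fall from 51 to 49 stays uncounted.

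**Shift classes.** A minimum LVEF of exactly 50% belongs to both the 40% to 50% class and the >=50% class.

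**The case against.** The best case against is that little is lost from view.

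- **Phosphate is reported elsewhere.** Beyond the maximum, change-from-baseline and special-interest summaries, high phosphate can surface in TEAEs leading to interruption or adjustment, TEAEs needing additional medication, and reasons for dose change. Protocol 6.3.1 directs treatment in the >5.5 to 7.5 mg/dL band unless local practice differs, so many such values would become AEs. This stands, but these are event counts. None says how many patients exceeded a given mg/dL level.
- **The wording may allow a table.** SAP 2.7.2.2.1 permits low/normal/high or project-specific ranges where grades are not defined. Tables 4 and 5 are only examples, and the table shells are not in the documents. This stands as a limit: a high-direction table is not excluded. But the provision is written for tests without grades, so the SAP does not specify one for phosphate.
- **The AE-grading step is inferred.** It relies on Table 4 reflecting how CTCAE 4.03 treats high phosphate, and that source is not in the documents. This is fair, and it is stated as an assumption below.
- **The 7.5 mg/dL level is not a plain cut-point.** Protocol Table 5 ties it to more than 7 days and maximal therapy. A 7.0 figure appears in the same row's restart text, and 6.3.1 uses >=7.5. This is correct. A row of single values would not count patients who meet the hold rule.
- **LVEF impact is small.** The shift table places every patient by level, change from baseline is summarised, and Protocol Table 7 schedules post-baseline imaging only at Cycle 2 Day 1 and end of treatment. The 19% weights grid cells equally. This limits the practical impact. It does not repair a definition that drops worse cases, and the shift table does not show the size of the fall.

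**Conclusion.** Both parts hold.

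For phosphate, the SAP specifies no grade, shift or high/low laboratory table that shows high values. The grade tables it does specify return Grade 0 for all of them. The gap is confined to categorical laboratory tables; continuous and AE summaries remain. The reading rests on SAP Table 4 for the direction of grading and on the SAP text alone, without the shells.

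For LVEF, the categories are neither exhaustive nor monotone. The counter-examples from baselines 65% and 55% need no assumption about the baseline distribution. The grid share is 19%, ranging from 15.5% to 22.1% as the assumed ceiling moves from 65 to 75. It describes the rule and does not forecast patient numbers.

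No efficacy estimate or decision rule is affected. This should be corrected because the tables concern expected or monitored toxicities and can mislead as written.

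**What to change.** **Phosphate**
- Label the graded phosphate tables as low direction only.
- Add a high-direction worst-value and shift table by normal range.
- Tabulate worst post-baseline phosphate at >5.5, >7.5 and >9.0 mg/dL. State that these rows count measured values, not patients meeting a dose-hold criterion. The 7.0 and 7.5 mg/dL figures in protocol Table 5 and Section 6.3.1 must be reconciled before the row labels are final.

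**LVEF**
- Keep the joint requirement of a fall >10 points and LVEF <50%.
- Assign each such case to the worse of its fall-size category and its level category, with LVEF <20% highest.
- Show falls >=20 points with LVEF still >=50% (for example 80% to 60%) as a separate row.
- Write the shift classes as <40%, 40 to <50% and >=50%.

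The cost is SAP wording and two table shells. All the data are already collected.

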2.7.2.2.2 Imputation Rules

CTC grading for blood differentials is based on absolute values.

If laboratory values are provided as ' $<X$ ' (ie, below limit of detection) or ' $>X$ ', prior to conversion of laboratory values to SI unit, these numeric values are set to X.

The following rules will be applied to derive the WBC differential counts when only percentages are available for a xxx differential

$$\text{xxx count} = (\text{WBC count}) * (\text{xxx \%value} / 100)$$

Corrected calcium can be derived using the reported total calcium value and albumin at the same assessment. The adjustment is done on calcium where albumin is less than 40 g/L and doesn't adjust when albumin ≥ 40 g/L because it can lead to underestimation. The formula for adjustment based on SI unit is:

When Albumin ≥ 40 g/L, then Corrected Calcium (mmol/L) = Calcium (mmol/l);

When non-missing Albumin <40 g/L, Corrected Calcium (mmol/L) = Calcium (mmol/L) + 0.02 \times (40-Albumin(g/L))

In the formula above, SI unit mmol/L and g/L for Calcium and Albumin are used, respectively. The normal range of corrected calcium is same as the calcium's.

CTC grades for the derived absolute WBC differential counts (neutrophils, lymphocytes) and corrected calcium are as defined in the previous section.

2.7.2.2.3 Data Analysis

The laboratory summaries will include all assessments available for the lab parameter collected no later than 30 days after the last study treatment administration date. Laboratory parameters for hematology and blood chemistry will be summarized at baseline, each post-baseline visit (based on the visit schedule defined in the protocol along with a window), the maximum and minimum observed post-baseline values, and last observed value, along with the change from baseline.

For laboratory tests where grades are defined by CTCAE 4.03:

- Worst post-baseline CTCAE grade (regardless of the baseline status). Each subject will be counted only once for the worst grade observed post-baseline.
- Shift tables using CTCAE 4.03 grades to compare baseline to the worst on-treatment value

For laboratory tests where grades are not defined by CTCAE 4.03, the summary will be based on normal range:

- Worst post-baseline abnormal value (regardless of the baseline status). Each subject will be counted only once for the high/low category.
- Shift tables to compare baseline to worst on-treatment values using the low/normal/high/ (low and high)

For laboratory tests that are graded for both low and high directions, the shift tables and summary of post-baseline abnormal results will be done separately and labeled by direction.

As discussed in ‘Minimum Critical Toxicities’ in Section [2.7.2.1.2](#), incidence of potential drug-induced liver injury based AST, ALT, TBL, ALP will be presented and potential Hy’s law cases will also be listed.

[Table 4](#) provides an example of laboratory parameters for which CTCAE grades are defined, [Table 5](#) provides an example of laboratory parameters for which shift tables were based upon the local lab normal range

Table 4: Example of Laboratory Parameters for Which CTCAE Grades are Defined

| Hematology and Coagulation | Biochemistry | |
|----------------------------|--------------|-------------------------------|
| White Blood Cells (WBC) | ↑ ↓ | Creatinine ↑ |
| Hemoglobin | ↑ ↓ | Sodium ↑ ↓ |
| Platelets counts | ↓ | Potassium ↑ ↓ |
| Absolute Neutrophils | ↓ | Corrected Calcium ↑ ↓ |
| Absolute Lymphocytes | ↑ ↓ | Magnesium ↑ ↓ |
| APTT | ↑ | Albumin ↓ |
| INR | ↑ | AST (SGOT) ALT (SGPT) ↑ |
| | | Total Bilirubin ↑ |
| | | Phosphate ↓ |
| | | amylase ↑ |
| | | lipase ↑ |
| | | Alkaline phosphatase ↑ |
| | | Total Cholesterol ↑ |
| | | Triglycerides ↑ |
| | | Urate ↑ |

↑ Indicates that CTC grade increases as the parameter increases.

↓ Indicates that CTC grade increases as the parameter decreases.

Table 5: Examples of Laboratory Parameters (Without CTCAE Grades) for Which Lab Reference Ranges Are Defined

| Hematology and Coagulation | Biochemistry |
|----------------------------|---------------------------|
| Prothrombin time (PT) | Blood urea nitrogen (BUN) |
| Hematocrit | Urea |
| Absolute Basophils, | Total protein |
| Absolute Eosinophils | Direct Bilirubin |
| Absolute Monocytes | Indirect Bilirubin |
| | Chloride |
| Red Blood Cells (RBC) | |

